4.5.2 Exclusion Criteria

1. Pregnancy or lactation
2. Liver impairment (ALT, AST or Bilirubin > 2 ULN) at screening visit or baseline
3. Kidney impairment (serum creatinine > 1.5 mg/dL)
4. History of congestive heart failure (NYHA III & IV)
5. History of malignant disease within 5 years
6. History of any disease or relevant physical or psychiatric condition or abnormal physical finding which may interfere with the study objectives at the investigator judgment
7. Known hypersensitivity to the investigational drug or any of its components
8. Participation to another clinical trial within 4 weeks before study inclusion except for patients who have participated or who are currently participating in an interventional study without any study drug administration.

4.6 Demographic and Baseline Characteristics Assessments

Demographic data is collected at Visit V0 (Screening/Baseline) and include month and year of birth, age in years, gender (Male or Female) and ethnicity. This data also includes:

- Medical history
- Results of pregnancy test
- Physical examination (including height, weight and BMI)
- Vital signs (blood pressure, heart rate)
- Previous and current medications (taken at least two weeks before the screening visit and those ongoing at screening), including the RA and AS treatment
- Electrocardiogram (ECG) 12-lead
- Laboratory assessment (haematology, biochemistry, urinalysis)
- Immunogenicity (by ELISA)

4.7 Previous, Current and Concomitant medication assessments

Any previous and concomitant medications (including the specific RA/AS treatments as per the protocol) are recorded at visit V0 (taken at least two weeks before the screening visit and those ongoing at screening) and at each subsequent visit. At subsequent visits, only new therapy or changes in therapy since the previous visit are recorded.

4.8 $^{99}\text{m}\text{Tc}$ -DPD-bone scintigraphy and whole body planar imaging

All patients will have a baseline DPD- $^{99}\text{m}\text{Tc}$ bone scan if not already performed within 8 weeks before rhAnnexin V-128 administration.

Then a whole body planar imaging will be performed prior to any treatment.

4.9 Safety

4.9.1 Adverse Events

AEs will be reported from signing the informed consent onwards until the last study-related procedure. If the information of an untoward medical occurrence is collected before starting the intake of study medication, this information will be listed as a pre-treatment AE during statistical analysis. AEs that occurred after the first intake of study medication will be considered as treatment emergent for the analysis.

All AEs occurring during the study are to be followed up until resolved or judged to be no longer clinically significant, or until they become chronic to the extent that they can be fully characterized. An assessment should be made at the last study-related visit for each patient (See Study Protocol for more details).

4.9.2 Laboratory Parameters

Laboratory tests (haematology, coagulation, blood chemistry and urinalysis) will be monitored before and after the Day 1 visit, with additional samples at 24 hours (only for patients participating to the PK substudy), 30, 42 and 90 study day.

4.9.3 Vital Signs, Physical Examination and ECG

Vital signs will be recorded at each study visit.

Physical Examination will be performed at screening, 42 and 90 study day.

Twelve-lead ECG will be performed at screening, dosing (Day 1), 24 hours (only for patients participating in the substudy), 30, 42 and 90 study day.

4.10 Pharmacokinetics and Dosimetry

For first 3 patients included into the subgroup of PK and dosimetry study, blood sample will be collected at Day 2 For the first 3 patients participating to the PK substudy, a further 10 ml of venous blood samples will be drawn at nominal times of 0, 5, 10, 15, 30, 60 minutes as well as 2 hrs, 4hrs and 24 hrs post administration. Depending upon the results in those 3 patients, the timeframe for dosimetry measurements and PK will be confirmed or modified with a time-point at 3 hrs (instead of 2 hrs) and 6 hrs (instead of 4 hrs) for the following 7 enrolled patients in the sub-study.

Urine sample will be collected within 24 hrs prior to ^{99m}Tc -rhAnnexin V-128 administration, preferable just prior to its administration (0 h sample) to achieve bladder emptying. Urine collections will be obtained and volume recorded, possibly in the time intervals 0-1 h, 1 h – 4 hrs, 4 hrs -16 hrs, 16 hrs – 24 hrs post administration. Dual 2 mL aliquots of urine from each period will be counted in a gamma counter at local laboratory

4.11 Immunogenicity

Assays for anti-rhAnnexin V-128 IgG and IgM antibodies will be performed in serum samples by ELISA. For this purpose 10mL blood samples will be collected at baseline, at Day 30 ± 3 days and at Day 56 ± 14 days. An additional sample is required 3 months after the first administration of the ^{99m}Tc -rhAnnexin V-128 (Day 90 ± 14 days) in case of positive anti-Annexin antibodies outcome in previous examinations.

5 STUDY SCHEMA

Study Procedures	Screening (±4 weeks)	Day 1	24 hours ¹	Day 30 ±3 days	Day 42 ±2weeks	Day 56 ±2weeks	Day 90 ±2weeks
Written informed consent	x						
Inclusion/exclusion criteria	x						
Medical history	x						
Concomitant medications including RA and AS treatment	x	x	x	x	x	x	x
Disease assessment (BASDAI, BASFI, BASMI for AS for AS patients, DAS28 scales including Ultrasound assessments for RA patients)	x				x		x
Physical examination	x				x		x
Vital signs (BP and HR)	x	x	x	x	x	x	x
Lab analysis (haematology, biochemistry; urine)	x		x	x	x		x
Venous/urine sampling (PK and dosimetry) ²		x ¹	x				
Immunogenicity by ELISA ³	x			x		x	x
Urine SEC-HPLC analysis ^{1,4}		x	x				
Pregnancy test	x	x			x		
Standard 12-lead ECG	x	x	x	x	x		x
rh-Annexin V-128 administration ⁵		x			x		
Bone scintigraphy ⁷	x						
Whole Body scintigraphic imaging ⁵		x	x		x		
Adverse Events	x	x	x	x	x	x	x

6 STUDY ENDPOINTS

The following study endpoints are derived from the clinical study protocol objectives.

6.1 Safety endpoints (Primary)

Safety endpoints will be evaluated by:

1. Serious and non-serious adverse event assessments
2. Abnormal haematology, coagulation, blood chemistry, urinalysis laboratory tests
3. Change from baseline of ECG parameters (including HR heart rate, RR interval, PR interval, QRS width and QT interval)
4. Change from baseline of vital signs

6.2 Pharmacokinetics and Dosimetry (Secondary - only for patients participating to the dosimetry and pk substudy)

Pharmacokinetics and dosimetry will be assessed by:

1. Serial measurements of rhAnnexin V-128 concentrations (by ELISA) from serum samples
 - a. Annexin concentrations in serum
 - b. Annexin PK parameters: AUC, Vz, Cl and elimination t_{1/2}
2. Serial measurements of radioactivity in whole blood and serum samples
 - a. Whole blood and serum concentrations of total radioactivity
 - b. Whole blood and serum PK parameters for total radioactivity: AUC, t_{1/2}
3. Serial measurements of radioactivity in urine samples
 - a. % excretion of total radioactivity in urine
 - b. SEC-HPLC analysis – as a function of time to assess chemical status and presence of Annexin related species
4. Radiation dose to the organ of interests (particularly the kidneys), effective dose equivalent and effective dose

6.3 Immunogenicity

Immunogenicity will be evaluated by Anti-rhAnnexin V-128 IgG and IgM antibodies assessment (by ELISA) at baseline and at 30 and 56 days post-administration. An additional sample at 90 days will be taken only in case of positive anti-Annexin antibodies outcome in previous examinations.

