medicine imaging of 99mTc-rhAnnexin V-128 intravenous administration of 370 MBq single intravenous bolus in 12 healthy adult volunteers has been conducted. A series of images for up to 24 hours from the time of injection and blood samples were obtained from time of screening, dosing day and 24 hours after injection, with follow up visits at 72 hrs, 7 days and 30 days post injection. A physical examination was conducted 72 hrs, 7 days and 30 days post administration of 99mTc - rhAnnexin V-128. No abnormal findings have been noted after administration of the studied imaging product and during the observation period. No immunology response has been reported in any of the 12 treated subjects (15 and 30 days post administration). The Phase I Clinical Trial Report is in preparation.

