**Patients participating to the dosimetry and PK studies will undergo the following additional assessments:**

**Pharmacokinetics (blood and urine)**

Venous blood samples of 10 ml each will be taken just before administration of 99mTc-rhAnnexin V-128 and then at the following time-points: 5, 10, 15, 30, 60 min, 2 hrs, 4 hrs and 24 hrs post the first rhAnnexin V-128 administration for the first 3 patients included in the sub-study. Depending upon the results in those 3 patients, the timeframe for dosimetry measurements and PK will be confirmed or modified with a time-point at 3 hrs (instead of 2 hrs) and 6 hrs (instead of 4 hrs) for the following 7 enrolled patients in the sub-study. The following whole blood or serum aliquots will be prepared as described in Appendix 2:

- 1) 2 x 1 mL of whole blood will be used for radioactivity measurements
- 2) 2 x 1 mL of serum aliquots will also be used for radioactivity measurements
- 3) 2 x 0.6 mL at least of serum aliquots to be frozen at -80°C, will be used for pharmacokinetics measurements. After complete decay of radioactivity, one out of 2 aliquots/time-point will be shipped to the centralized laboratory and analyzed by ELISA to determine the rhAnnexin V-128 concentration in serum (See the Laboratory Manual for further instruction).

The whole blood and serum samples (bullet points 1 and 2) will be counted in a gamma counting system (CHUV/NUC laboratory) and compared to the count rate from a representative percentage of the injected activity inside the same counter.

Blood clearance fractions and effective half-life estimates from multi-term non-compartmental exponential analysis will be calculated from serial measurements of radioactivity in whole blood and serum. Pharmacokinetic analysis will be also performed based on rhAnnexin V-128 serum concentration determined by ELISA method.

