### **Sample size**

The number of patients in this study is not based on statistical power considerations. The planned sample includes 20 patients with Day 56 assessments which are believed to provide sufficient data to assess the general safety and tolerability of 99mTc-rhAnnexin V-128. Patients will be recruited with a ratio of 1:1 RA:AS.

Any patient who has not completed Day 56 assessment will be replaced by a patient from the same group (RA or AS). It is expected that about 10% of patients will not complete their Day 56 assessments; therefore, approximately 23 patients will be recruited.

In addition, 10 patients enrolled in the study will be asked to participate in a dosimetry and PK study, irrespective of the group they are part of (RA or AS).

Out of the first 6 patients, at least 3 patients must take part in the dosimetric and PK sub-study.

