6.5 Imaging assessments

To assess the suitability of 99mTc-rhAnnexin V-128 imaging for detecting RA or AS lesions before and after short term treatment by observing qualitatively the number and location of lesions at each imaging point and calculating the intensity of lesion uptake (specific) as well as quantitatively through assessment of radiotracer uptake by geometric mean of counts/ROI on anterior and posterior planar images. Only patients with available anterior and posterior planar imaging data at 1h and at 2h post-injection at both Day 1 and Day 42 assessments will be considered for this analysis.

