14.3.5	Disease Assessment (BASDAI, BASFI, BASMI, DAS28, ACR/EULAR scores) at each visit and change from baseline	Safety
14.3.6	Listing of Anti-Annexin V-128 IgG and IgM antibodies Reactive results	Safety
14.3.7	Physical examination at each visit	Safety
14.3.8.1	Vital signs at each visit and change from baseline	Safety
14.3.8.2	Vital signs – Shifts from baseline	Safety
14.3.9.1	Overall Electrocardiogram interpretation	Safety
14.3.9.2	Electrocardiogram parameters at each visit and change from baseline	Safety

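### Antibody results are not linked to the Day 1 versus Day 42 scan comparison, so an effect of re-exposure could be misread as a treatment effect or could mask one

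*SAP*

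**What the plan says.** **Antibodies.** SAP 6.3 states: "Immunogenicity will be evaluated by Anti-rhAnnexin V-128 IgG and IgM antibodies assessment (by ELISA) at baseline and at 30 and 56 days post-administration". A Day 90 sample is added only after an earlier positive. SAP 7.15 plans a descriptive table of these results. The list of tables in SAP 10.1 contains one antibody item, Table 14.3.6, "Listing of Anti-Annexin V-128 IgG and IgM antibodies Reactive results". Its shell has four columns: subject, visit, result and optical density (OD). SAP 10.3 adds a by-subject listing of all immunogenicity results (16.2.4.16).

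**Imaging.** SAP 6.5 sets out to judge whether the scan is suitable "for detecting RA or AS lesions before and after short term treatment". Its quantitative measure is the geometric mean of anterior and posterior counts per region of interest. It also mentions the intensity of specific lesion uptake, without defining it. Patients enter this analysis if they have 1 h and 2 h planar images at both Day 1 and Day 42. SAP 7.17 relates the scans to the disease scores only. The Imaging part of protocol section 6 plans a target-to-background ratio (TBR) and the relative uptake before and after treatment.

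**Kinetics.** In the sub-study, serial blood samples are timed "post the first rhAnnexin V-128 administration". The sampling schedules in protocol Appendix 2 are likewise tied to the first injection.

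**Design.** Protocol section 3 has one open-label cohort, two injections about six weeks apart, and a new RA or AS therapy from Day 2 for everyone.

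**The concern.** Three things change together between the two scans: time passes, a new therapy starts, and the patient goes from first to second exposure to the tracer protein. With no control group, the comparison cannot separate them. Antibodies that are present at the second injection could bind the tracer and change how much reaches the joints or stays in the background. That change would sit inside the Day 1 to Day 42 difference.

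The protocol's hypothesis is that the scan might help to judge response to therapy, so a change in uptake will be read with that in mind. An antibody-related fall could look like improvement, and an antibody-related rise could conceal it. The trial already collects the data needed to flag the patients concerned, and protocol section 7 asks the data monitoring committee to look at immunologic results when it judges technical performance. The imaging analysis does not use them.

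**Working it through.** **1. The plan's own figure.** The protocol says: "It is expected that about 10% of patients will not complete their Day 56 assessments; therefore, approximately 23 patients will be recruited". Check: 20/(1 − 0.10) = 22.2, rounded up to 23. It reproduces. The point here does not depend on it, and linking antibody status to the scan does not change the sample size.

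**2. Inputs.** Planned evaluable patients: 20 (protocol section 8, "The planned sample includes 20 patients with Day 56 assessments"). After recruitment stopped early, SAP 4.2 refers to 80% or more of this: 0.80 × 20 = 16. Earlier antibody data (protocol section 1): "No immunology response has been reported in any of the 12 treated subjects", that is 0/12 after a single dose in healthy volunteers.

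**3. What 0/12 allows.** The exact two-sided 95% upper limit is 1 − 0.025^(1/12) = 0.265, or 26.5%. The one-sided 95% limit is 1 − 0.05^(1/12) = 0.221, or 22.1%.

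**4. Chance of at least one positive patient**, 1 − (1 − p)^n, for assumed incidences p (the documents give none):

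| Assumed p | n = 16 | n = 20 |
|---|---|---|
| 2% | 27.6% | 33.2% |
| 5% | 56.0% | 64.2% |
| 10% | 81.5% | 87.8% |
| 20% | 97.2% | 98.8% |

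**5. Effect on a group mean.** If one patient's measured uptake moves by an assumed s, in either direction, the mean relative change moves by s/n. For s from 20% to 50%:
- n = 20: 1.0 to 2.5 percentage points
- n = 16: 1.25 to 3.1 points
- a disease group of 10: 2.0 to 5.0 points

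That patient's own before/after result moves by the full 20% to 50%. The imaging set may be smaller than 16, because SAP 6.5 needs 1 h and 2 h images at both visits. The chance of including a positive patient is then lower, and the shift per positive patient is larger.

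**6. Timing of the antibody samples.**
- Day 30 sample: 30 ± 3, Day 27 to 33
- Second injection: 42 ± 14, Day 28 to 56
- Day 56 sample: 56 ± 14, Day 42 to 70

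The Day 30 sample can therefore fall after the second injection (overlap Day 28 to 33) or precede it by up to 56 − 27 = 29 days. Visit labels alone do not give antibody status at the second scan; the dates are needed.

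**7. What Table 14.3.6 would show.** Only reactive results are listed, and IgG and IgM are not distinguished in the shell. A patient who is non-reactive at screening and reactive later has no baseline row, so the rise in OD cannot be read from this table.

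**The case against.** The case on the other side is substantial, and most of it limits the point rather than removing it.

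- **A reader might infer that altered clearance would be counted as a response, and that the bias favours response.** The documents do not support either. They define no responder, no threshold of change and no response count, and the imaging analysis is descriptive. They do not say that antibodies alter this tracer's clearance, and the direction is unknown. Annexin V is an endogenous human protein, and the product is a mutant with six added amino acids.
- **A reader might infer that the reactive listing is the only antibody output.** It is not: SAP 7.15 plans a descriptive table and Listing 16.2.4.16 covers all results, so a cross-check by hand is possible. It is not specified.
- **A reader might infer that nothing else could reveal altered kinetics.** The 1 h and 2 h images at both visits allow some comparison of early change over time, and the protocol's TBR offsets part of a general change in tracer availability. This protection is partial, and SAP 6.5 does not carry the TBR forward.
- **A separate PK/immunology analysis plan is promised in protocol section 8.** It was not supplied, so the gap is established only for the protocol and SAP. Neither SAP 6.3 nor SAP 7.15 refers to such a plan, and the imaging analysis is specified in the SAP.
- **The data monitoring committee sees immunologic results.** That is oversight during the trial, not an analysis of scan change.

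**Conclusion.** The point holds in a limited form. In the protocol and SAP supplied, antibody status is not linked to the before/after imaging comparison, while re-exposure and new therapy coincide and kinetics are sampled after the first injection only. An antibody-related change in uptake could be misread as a treatment effect or could mask one.

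The size cannot be stated from the documents. Zero of 12 is compatible with a true incidence up to 26.5%, in a different population and without re-exposure. At an assumed 5%, at least one positive patient is more likely than not (56% to 64%). The size of any effect on uptake is wholly an assumption. On a group mean, one such patient matters little to moderately; on that patient's own result, it could matter a great deal. Combining the upper limit with a large assumed effect would give a worst case, not an estimate. The change is worth making because it is cheap and uses data already planned.

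**What to change.** 1. In SAP 6.5 and 7.17, show antibody status beside each patient's before/after imaging result, for IgG and IgM separately and against the patient's own baseline. Take it from the last sample dated before the second injection. Mark it as baseline only where the Day 30 sample came after that injection. Show the first sample after the second injection alongside.
2. Report the protocol's TBR next to counts per region.
3. Repeat the before/after summary without patients who are newly reactive or have risen above their baseline. Patients reactive at baseline and unchanged stay in, with the flag. State the rule for a rise in OD beforehand; the documents supplied give no cut-point.
4. In Table 14.3.6, add an IgG/IgM column and each listed patient's baseline result and OD.

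Cost: SAP wording, a few extra columns and one repeated descriptive table. No new samples or visits are needed, and the sample size does not change. The repeat summary uses slightly fewer patients and, with 16 to 20 at most, can only be descriptive. It can show whether the imaging result depends on these patients; it cannot prove that antibodies caused a change.

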6.4 Disease Assessment

BASDAI (Bath Ankylosing Spondylitis Disease Activity Index), BASFI (Bath Ankylosing Spondylitis Functional Index) and BASMI (Bath Ankylosing Spondylitis Metrology Index) scores for AS patients will be presented as a descriptive table at each visit.

DAS28 and ACR/EULAR scores for RA patients will be presented as a descriptive table at each visit.

6.5 Imaging assessments

To assess the suitability of 99mTc-rhAnnexin V-128 imaging for detecting RA or AS lesions before and after short term treatment by observing qualitatively the number and location of lesions at each imaging point and calculating the intensity of lesion uptake (specific) as well as quantitatively through assessment of radiotracer uptake by geometric mean of counts/ROI on anterior and posterior planar images. Only patients with available anterior and posterior planar imaging data at 1h and at 2h post-injection at both Day 1 and Day 42 assessments will be considered for this analysis.

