99mTc-rhAnnexin V-128 administrations:patients will be injected intravenously with 250 MBq of 99mTc-rhAnnexin V-128 and then the whole body planar imagings (GE Infinia Hawkeye IV camera, (8 cm/min, 1024x256 matrix; zoom 1) will be performed and repeated acquisitions on symptomatic joints. Standard quality control of the camera will be performed every day before patient imaging. Peak will be centered on 140KeV with a 20% windowing; a LEHR collimator will be used. A dual-SPECT would be acquired centered on the thorax and abdomen at 1h after injection centered (2\*60 projections of 10 seconds each, 128x128 matrix, zoom 1). The use of the whole-body and SPECT data for dosimetry will be discussed further in the Dosimetry section

Semi-quantitative assessment of inflammatory joints will be performed in terms of TBR as well as by calculating the relative uptake between pre and post treatment in ROI/VOIs. ROI and VOI defined and use in the different scintigraphies will strictly have the same pixel size and localization; they will be measured in counts.

In case a suspected anomaly is found at imaging, it would be reported to the rheumatologist and the patient's general practitioner.

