
For each source region, the measured activity at each time point will be normalized to that administered, decay-corrected to the time of injection, and least-squares-fit by an analytical function. Physical decay of 99mTc will then be introduced to these analytical fits of the normalized activities and the function integrated to yield the cumulated activity normalized to the amount of administered activity (numerically equivalent to the residence time). The cumulated activity in the combined urinary bladder contents and voided urine will be calculated using a dynamic urinary bladder model [33] for a 3.5 hour urinary bladder voiding interval [34]. The cumulated activity in the gastrointestinal tract [35] with the assumption that all activity enters the duodenum via the hepatobiliary transport will be calculated.

Radiation dose to the organ of interests (particularly the kidneys), Effective Dose Equivalent (ICRP 30), Effective Dose (ICRP 60) will also be calculated.

The internal radiation dosimetry for the adult human will be calculated through the normalized cumulated activities for each patient provided as input to OLINDA. The derived ensemble of organ absorbed doses will then be used to calculate the Effective Dose per unit administered activity [36] with the following modifications: 1) gonadal absorbed dose will be taken to be the arithmetic mean of the testicular and ovarian absorbed doses [34]; 2) absorbed dose to the thymus will be used as a surrogate for the absorbed dose to the oesophagus [36]; and 3) absorbed dose to the wall of the upper large intestine will be removed from the remaining organs category and the mean absorbed dose to the colon

wall, given by the mass-weighted absorbed doses to the walls of the upper and lower large intestine, used in the Effective Dose [36].

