7.1.5.2 Derivation of Activity Measurement of Effective administered dose (MBq)

Activity measurement of the effective administered dose is derived as the difference between the measured radioactivity of the pre-injection total dose in the syringe (in MBq) and the measured radioactivity of the post-injection residual dose remaining in the syringe (in MBq).

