7.6 Extent of Exposure

Summary statistics of the volume of drug injected in mL as well as the actual dose in MBq and MBq/kg will be summarized in the safety dataset by RA/AS patient disease groups and total and by 1st and 2nd injection.

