7.16 Disease Assessment

BASDAI, BASFI and BASMI scores for AS patients will be presented as a descriptive table at each visit.

DAS28 and ACR/EULAR scores for RA patients will be presented as a descriptive table at each visit.

7.17 ^{99m}Tc -rhAnnexin V-128 Scintigraphy

Descriptive statistics of the imaging findings with report of location and intensity of lesions at each imaging time point will be reported to determine the most suitable imaging time point post injection.

An association between annexin scintigraphy results and disease assessments (see Section 7.16) will be presented to assess diagnostic concordance.

These analyses will be taken care of by AAA's study physician and results will appended to the clinical study report.

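### SAP 6.5 measures before/after uptake as counts per region of interest, without dividing by the activity given at each of the two injections

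*SAP*

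**What the plan says.** SAP 6.5 has a qualitative part (number and location of lesions, and an intensity of specific lesion uptake that is not defined) and a quantitative part, the "geometric mean of counts/ROI on anterior and posterior planar images". Its entry rule is: "Only patients with available anterior and posterior planar imaging data at 1h and at 2h post-injection at both Day 1 and Day 42 assessments". Each patient therefore contributes images from two injections about six weeks apart.

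Elsewhere the documents handle activity as follows:

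- **Protocol section 6, Imaging.** "Semi-quantitative assessment of inflammatory joints will be performed in terms of TBR", and also as relative uptake before and after treatment. Regions are matched in size and position between scans and read in counts.
- **Protocol section 6, Dosimetry (sub-study organs).** "For each source region, the measured activity at each time point will be normalized to that administered, decay-corrected to the time of injection".
- **SAP 7.1.5.2.** "Activity measurement of the effective administered dose is derived as the difference" between the syringe readings before and after injection.
- **SAP 7.6.** The only stated use of that quantity: "the actual dose in MBq and MBq/kg will be summarized in the safety dataset", by first and second injection.
- **SAP 7.17.** Imaging findings are described at each time point "to determine the most suitable imaging time point post injection". The work falls to the sponsor's "study physician and results will appended to the clinical study report".

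SAP 6.5 and 7.17 mention neither TBR nor any scaling of counts to administered activity.

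**The concern.** Counts in a region rise and fall with the activity injected as well as with the tissue's uptake. A comparison within one injection is not affected by the amount given. A comparison across two injections is, unless the counts are scaled or expressed as a ratio to background from the same scan. As written, the quantitative measure can report a change after treatment that reflects only a different injected activity, or can mask a real one.

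At stake is the quantitative part of one secondary objective: evaluating lesions before and after short-term treatment. The imaging analyses are run outside the main statistical programming, so a clear written definition helps whoever carries them out.

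**Working it through.** **Inputs.**

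- Target activity is 250 MBq at each injection (Protocol Synopsis, Treatment; SAP 4.4). No tolerance is stated for it. The ±74 MBq in Protocol section 5 belongs to the 740 MBq added to the vial, not to the amount injected.
- The injected volume is calculated for the expected injection time, with half-life 6.02 h (Protocol section 5, Handling of Study Medication).
- 20 patients were planned and at least 80% are evaluable (SAP 4.2): 0.80 × 20 = 16. This is a floor for evaluable patients, not a count of usable image pairs.
- Deviations from 250 MBq are assumed below, because the documents give none.

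The plan has no numerical figure for this measure to reproduce.

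**Step 1: what the ratio estimates.** Let A be administered activity and u the uptake per unit of activity. Assume the same region, camera settings and time after injection. Anterior counts are a·A·u and posterior counts p·A·u, so the geometric mean is G = √(a·p)·A·u. Then

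G(42)/G(1) = [A(42)/A(1)] × [u(42)/u(1)].

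With unchanged uptake this equals A(42)/A(1). Taking the geometric mean of the two views does not remove A.

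**Step 2: one patient, opposite deviations.**

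- 5%: 0.95/1.05 = 0.905 (-9.5%); 1.05/0.95 = 1.105 (+10.5%).
- 10%: 0.90/1.10 = 0.818 (-18.2%); 1.10/0.90 = 1.222 (+22.2%).

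**Step 3: group mean, independent random deviations.** The log-ratio SD per patient is √2 × SD per injection.

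- SD 5%: √2 × 0.05 = 0.071; divided by √16, 0.018.
- SD 10%: √2 × 0.10 = 0.141; divided by √16, 0.035.

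This component combines in quadrature with the other sources of variation.

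**Step 4: timing.** The decay factor is 0.5^(t/6.02).

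- An injection 30 min later than planned at one visit: 0.5^(0.5/6.02) = 0.944, or -5.6% in activity. If systematic, this does not average out.
- A 15 min difference in acquisition time: 0.5^(0.25/6.02) = 0.972, or -2.8%.
- From 1 h to 2 h within one injection: 0.5^(1/6.02) = 0.891. At equal times on both days this cancels in the before/after ratio, but not in a comparison of 1 h with 2 h counts.

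**Step 5: does scaling cure it?** G/A gives the ratio u(42)/u(1) directly. In a TBR, target and background both carry A, so A cancels. For example, with 225 and 275 MBq and unchanged uptake, the count ratio is 275/225 = 1.222, while the scaled ratio and the TBR ratio are both 1.00.

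**Step 6: the entry rule.** Protocol Table 1 (footnote 5) fixes 1 h and 2 h on Day 1 for 3 + 3 = 6 patients. It leaves later Day 1 times and all Day 42 times to early results. Imaging at 1 h and 2 h on both days is a permitted outcome. Suppose, for illustration, that availability is 0.95 or 0.90. If the images of one visit are present or missing together, the four-image rule keeps 16 × 0.95² = 14.4 or 16 × 0.90² = 13.0 patients, the same as requiring a single same-time pair. If each image were missing independently, it would keep 16 × 0.95⁴ = 13.0 or 16 × 0.90⁴ = 10.5. Any loss from the rule therefore depends on an assumption the documents cannot settle.

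**The case against.** The best reply is that TBR is still in force. The SAP rests on the protocol, SAP 7.19 declares no changes to the planned analysis, and the undefined specific-uptake intensity in 6.5 could be TBR. That is plausible, and it means one should not say that TBR has been abandoned. It does not remove the gap. Counts per region is still the stated quantitative measure, the protocol's own before/after relative uptake is read in counts too, and background subtraction alone would not remove the injected activity.

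The second reply is about size. Both injections aim at the same activity, every deviation above is assumed, and random ones largely average out. The objective speaks of the presence of lesions, which number and location address without any scaling. No threshold, power figure or confirmatory test depends on the counts. All of this stands and sets the severity.

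Third, the administered MBq is derived, and study treatment administration is listed by subject (listing 16.2.5.1), so the counts could be rescaled later. That makes the change cheap. It is still better to define the measure before the results are seen.

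A reader might also infer that the 1 h and 2 h rule contradicts the protocol schedule, or that it shrinks the analysis to a known few. The documents do not support this. The protocol delegates imaging times to early results. The SAP's initial version is dated 26/01/2018, after recruitment was stopped by the end of September 2017, and SAP 4.2 foresaw a data review before finalisation. The rule may simply record the times adopted. Keeping the same patients at both times also suits the comparison in SAP 7.17, so complete sets versus available pairs is largely a trade-off.

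**Conclusion.** The point holds as a minor one. SAP 6.5 compares counts across two injections without scaling to the activity given at each, although the quantity needed is already derived and the protocol already normalises organ data in this way. The single-patient shifts in Step 2 need opposite errors at the two visits and should not be read as the expected bias. The group-level component in Step 3 is modest, and only a systematic difference between visits would carry through to the mean.

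These sizes rest on assumed deviations, on counts being proportional to administered activity, and on 16 patients contributing pairs. Primary safety and the qualitative lesion assessment are unaffected. No finding is made that the entry rule conflicts with the schedule. The 6 patients with both times fixed on Day 1 are the minimum the wording guarantees, not an estimate of the number analysed.

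**What to change.** In SAP 6.5, with a cross-reference from 7.17:

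- Define uptake as the geometric-mean region counts divided by the administered MBq of that injection (7.1.5.2), decay-corrected to injection using actual acquisition times where recorded.
- Report TBR alongside, as the protocol's Imaging section plans. TBR would also move if background uptake changed, so the two measures complement each other.
- Optionally, add a supplementary before/after summary of all same-time Day 1/Day 42 pairs, with n shown for each time, next to the complete set.

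The cost is SAP wording, a little more analysis work and a background region on existing images. No new images or patients are needed. In the optional summary, n may differ between time points, so 1 h and 2 h should be compared in the complete set only.
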